8. PHARMACOKINETIC ANALYSES

The PK analyses will be based on the “Pharmacokinetic” population.

8.1. Overview of Planned Pharmacokinetic Analyses

- Linear and semi-logarithmic individual plasma concentration-time profiles will be produced for each subject. Time will be relative to the first dose of study treatment. Individual plasma concentration-time profile plots grouped by baseline mepolizumab use and by baseline mepolizumab use and injection site (performed only for the subset of subjects using the same injection site throughout the study) will also be produced.
- Plasma concentrations will be listed and summarised by nominal time and by nominal time and baseline mepolizumab use. Mean (\pm SD) and median profiles by nominal time and baseline mepolizumab use will be plotted.
- Summaries of plasma concentration-time data will also be produced by baseline mepolizumab use and injection site, and mean (\pm SD) and median concentration-time profiles by baseline mepolizumab use and injection site will be plotted. These summaries will be performed only for the subset of subjects using the same injection site throughout the study.
- Refer to Appendix 3: Data Handling Conventions, Section 14.3.2 Reporting Process & Standards.

Table 4 provides an overview of the planned pharmacokinetic data displays. Full details of the data displays to be presented are given in Appendix 8: List of Data Displays.

Table 4 Overview of Planned Pharmacokinetic Analyses

Endpoints	Stats Analysis			Summary		Individual	
	F	T	L	F	T	F	L
PK Plasma Concentrations				Y ^[1] ^[2]	Y	Y ^[1]	Y

NOTES :

- T = Table, F = Figures, L = Listings, Y = Yes display generated.
 - Stats Analysis = Represents TFL related to any formal statistical analyses (i.e. modelling) conducted.
 - Summary = Represents TFL related to any summaries (descriptive statistics) of the observed raw data.
 - Individual = Represents FL related to any displays of individual subject observed raw data.
1. Linear and Semi-Log plots will be created on the same display.
 2. Separate Mean (\pm SD) and Median plots will be generated.

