Three doses of mepolizumab liquid drug product in safety syringe will be self-administered by the subject/caregiver at 4-weekly intervals; 2 doses will be administered under observation in the clinic (at Visits 2 and 4). The second in clinic administration (Visit 4) will not include any onsite training or support, other than the IFU, which could assist the subject. One dose will be administered outside the clinic and without observation (within 24 hours after attending the clinic for Visit 3). Following each injection, subjects will complete a patient diary, included in the Study Reference Manual (SRM), and report the pain experienced immediately following, 1- and 24-hours post injection. Observations about the injection will be recorded by the investigators for the doses administered in the clinic using an observer checklist. For the unobserved dose administered at home, a similar checklist detailing the steps required to successfully administer the injection will be completed by the subject/caregiver. All injections will be assessed by the investigator for success based on:

- Direct observation of the self-administration using the investigator Observer Checklist if the mepolizumab dose was administered in the clinic, and inspection of the safety syringe
- Subject/caregiver completed checklist and inspection by the investigator of the returned safety syringe if the mepolizumab dose was administered outside the clinic

A self-administered injection is considered successful if the following criteria are met:

- Use of a correct injection site (abdomen/thigh or upper arm [caregiver only])
- Full dose administered: subject fully inserts the needle, slowly depresses the plunger until the stopper reaches the bottom of the syringe and activates the needle guard by moving the thumb up
- No observations are made with respect to the safety syringe, following inspection by the investigator, which indicates the full dose has not been dispensed

If the above criteria are met, the investigator will confirm the injection was successfully delivered.

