7.9. Pharmacokinetics

Blood samples for analysis of mepolizumab plasma concentration will be obtained as per the Time and Events table (Section 7.1). Samples obtained at Visits 2, 3, 4 and 5 should be drawn prior to dosing. The date and exact time of collection for each sample will be documented in the eCRF.

Details for collection and processing of samples may be found in the SRM.

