9.4.4. Pharmacokinetic Analyses

Pharmacokinetic analysis will be the responsibility of the Clinical Pharmacology Modeling & Simulation department within GSK.

PK concentrations will be presented in graphical and/or tabular form and will be summarized descriptively overall, by previous mepolizumab use (i.e. not receiving mepolizumab treatment at Visit 1 or receiving 100 mg SC mepolizumab administered for the treatment of severe eosinophilic asthma every 4 weeks for at least 12 weeks prior to Visit 1) and by injection site.

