2. SUMMARY OF KEY PROTOCOL INFORMATION

2.1. Changes to the Protocol Defined Statistical Analysis Plan

An additional analysis population was defined for reporting screen failures and inclusion/exclusion criteria deviations. This population is described in Section 4.

There are no other changes to the protocol defined statistical analysis plan.

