9.1. Overview of Planned Analyses for Blood Eosinophils

- Blood eosinophil values will be \log_e -transformed prior to summarising. Non-detectable values of 0 GI/L, will be replaced by half of the lowest observed detectable (non-zero) value in the study data set, prior to log transformation.
- Blood eosinophil values will be summarised by visit, and by visit and baseline mepolizumab use.
- Blood eosinophil values will also be summarised by visit, baseline mepolizumab use and injection site. These summaries will be performed only for the subset of subjects using the same injection site throughout the study.

Table 5 provides an overview of the planned analyses for blood eosinophils. Full details of data displays to be presented are given in Appendix 8: List of Data Displays.

Table 5 Overview of Planned Analyses for Blood Eosinophils

Endpoint	Untransformed						Log-Transformed							
	Stats Analysis			Summary		Individual		Stats Analysis			Summary		Individual	
	F	T	L	F	T	F	L	F	T	L	F	T	F	L
Absolute Blood Eosinophils					Y						Y	Y		
Ratio to Baseline Blood Eosinophils					Y						Y	Y		

NOTES :

- T = Table, F = Figures, L = Listings, Y = Yes display generated.
- Stats Analysis = Represents TFL related to any formal statistical analyses (i.e. modelling) conducted.
- Summary = Represents TFL related to any summaries (descriptive statistics) of the observed raw data.
- Individual = Represents FL related to any displays of individual subject observed raw data.

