14.8.3. Pharmacokinetic Analyses

No.	Population	IDSL / TST ID / Example Shell	Title	Programming Notes	Deliverable [Priority]
PK Concentration: Figures					
8.1	PK	PK16a	Individual Plasma Mepolizumab Concentration-Time Plots (Linear and Semi-Log) by Subject	Subject number and baseline mepolizumab use as by-line. Indicate the injection site used for each dose using different plotting characters.	SAC
8.2	PK	PK26	Individual Plasma Mepolizumab Concentration-Time Plots (Linear and Semi-Log) by Baseline Mepolizumab Use	Baseline mepolizumab use as a by-line. All subjects in the same baseline mepolizumab group on the same graph ("spaghetti" plot).	SAC
8.3	PK	PK26	Individual Plasma Mepolizumab Concentration-Time Plots (Linear and Semi-Log) by Baseline Mepolizumab Use and Injection Site – Subjects Using the Same Injection Site Throughout the Study	Baseline mepolizumab use and injection site as a by-line. All subjects in the same baseline mepolizumab group and injection site on the same graph ("spaghetti" plot). Include only the subset of subjects using the same injection site for all doses of study treatment.	SAC
8.4	PK	PK17	Mean Plasma Mepolizumab Concentration-Time Plots by Baseline Mepolizumab Use (Linear and Semi-Log)		SAC
8.5	PK	PK18	Median Plasma Mepolizumab Concentration-Time Plots by Baseline Mepolizumab Use (Linear and Semi-Log)		SAC
8.6	PK	PK17	Mean Plasma Mepolizumab Concentration-Time Plots by Baseline Mepolizumab Use and Injection Site (Linear and Semi-Log) – Subjects Using the Same Injection Site Throughout the Study	Include only the subset of subjects using the same injection site for all doses of study treatment.	SAC

CONFIDENTIAL

205667

No.	Population	IDSL / TST ID / Example Shell	Title	Programming Notes	Deliverable [Priority]
8.7	PK	PK18	Median Plasma Mepolizumab Concentration-Time Plots by Baseline Mepolizumab Use and Injection Site (Linear and Semi-Log) – Subjects Using the Same Injection Site Throughout the Study	Include only the subset of subjects using the same injection site for all doses of study treatment.	SAC
Pharmacokinetic – Tables					
8.1	PK	PK01	Summary of Plasma Mepolizumab Concentration-Time Data		SAC
8.2	PK	PK01	Summary of Plasma Mepolizumab Concentration-Time Data by Baseline Mepolizumab Use		SAC

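### The Week 4 injection-site summaries of PK and eosinophils leave out every subject who later changes site, although the Week 4 sample is taken before dose 2

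*SAP*

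**What the plan says.** **The restriction.** SAP 8.1 states that PK plots and summaries by baseline mepolizumab use and injection site are "performed only for the subset of subjects using the same injection site throughout the study". For eosinophils, SAP 9.1 says: "Blood eosinophil values will also be summarised by visit, baseline mepolizumab use and injection site", and then: "These summaries will be performed only for the subset of subjects using the same injection site throughout the study". The programming notes in SAP 14.8.3 (PK Figures 8.3, 8.6 and 8.7; PK Table 8.3) define the subset: "Include only the subset of subjects using the same injection site for all doses of study treatment". SAP 14.8.4 carries the same note for PD Figures 9.2 and 9.4 and PD Tables 9.5 and 9.6. No visit is exempted.

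**The timing.** On PK, Protocol 7.9 says: "Samples obtained at Visits 2, 3, 4 and 5 should be drawn prior to dosing". Footnote d of the Time and Events Table (Protocol 7.1) also places the Week 4 haematology sample before dosing. Protocol 4.1 describes the second dose: "One dose will be administered outside the clinic and without observation (within 24 hours after attending the clinic for Visit 3". The site of each dose is recorded (Protocol 4.1, 6.8.1 and 6.8.2).

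**The protocol's plan.** Protocol 9.4.4 asks for PK summaries overall, by previous mepolizumab use and by site. Its wording ends "every 4 weeks for at least 12 weeks prior to Visit 1) and by injection site" and sets no same-site condition. Protocol 9.4.3 does likewise for the eosinophil ratio to baseline. SAP 2.1 declares one added analysis population and then says: "There are no other changes to the protocol defined statistical analysis plan".

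**The concern.** A same-site rule has a clear purpose when several doses contribute to a trough. If a subject used the abdomen and then the thigh, the Week 12 concentration belongs to neither site. That reasoning does not reach Week 4, when only dose 1 of study drug has been given.

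Applied at Week 4, the rule decides whether a value enters the site summary from choices made after the blood was drawn. This costs subjects for no pharmacological gain. It can also select, if the decision to change site is related to how dose 1 went. A subject who had pain or an incomplete first injection might move to another site, and that subject's Week 4 value would then drop out of the summary for the first site. The documents do not say whether this happens. The plan leaves room for it without need.

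At stake are the precision and representativeness of the Week 4 site summaries, and an undeclared narrowing of what the protocol planned.

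**Working it through.** **Step 1. Compare the doses that can affect each sample with the doses the rule uses.**

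| Sample | Study doses already given | Doses whose site the rule uses |
|---|---|---|
| Week 4 (Visit 3, pre-dose) | 1 | 1, 2, 3 |
| Week 8 (Visit 4, pre-dose) | 1, 2 | 1, 2, 3 |
| Week 12 (Visit 5) | 1, 2, 3 | 1, 2, 3 |

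At Week 12 the two columns agree. At Week 8 the rule looks one dose too far ahead, but a same-site condition on doses 1 and 2 is needed there in any case. At Week 4 no same-site condition is needed.

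**Step 2. Base number.** The plan gives no figure for the size of the same-site subset. Protocol 9.2.1 gives 55 enrolled, up to 10% dropout and at least 50 with complete data. 55 × (1 − 0.10) = 49.5, which agrees with the stated 50 after rounding. So about 50 to 55 subjects could contribute at Week 4.

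**Step 3. Share kept if subjects tend to stay with a site.** Let s be the probability of keeping the site at each of the two transitions (assumed). The share kept is s².

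| s | Share kept | Lost, of 50 to 55 |
|---|---|---|
| 0.95 | 0.9025 (90%) | about 5 |
| 0.90 | 0.81 (81%) | about 10 |
| 0.80 | 0.64 (64%) | 18 to 20 |
| 0.50 | 0.25 (25%) | 38 to 41 |

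**Step 4. Share kept if site is chosen afresh at each dose.** With two sites of share p and 1 − p (assumed), the share kept is p³ + (1 − p)³.

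- 90/10: 0.729 + 0.001 = 0.73, or 36.5 of 50.
- 80/20: 0.512 + 0.008 = 0.52, or 26 of 50.
- 50/50: 0.125 + 0.125 = 0.25, or 12.5 of 50.
- Three equally used sites: 3 × (1/3)³ = 0.11, or 5.6 of 50.

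Across both models the loss runs from 0% (nobody switches) to about 89%.

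**Step 5. Precision of one site's mean at Week 4.** Under Step 4, a site with share p keeps p² of its dose 1 users, so the standard error of its mean is inflated by 1/√(p²) = 1/p.

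- 90/10: 1/0.9 = 1.11 for the common site and 1/0.1 = 10 for the rare one.
- 80/20: 1.25 and 5. Of 50 subjects, the common site goes from 40 to 0.64 × 40 = 25.6, and the rare site from 10 to 0.04 × 10 = 0.4. In practice the rare site has no summary left.
- 50/50: 2.0 for each.

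Under Step 3 every site keeps s² of its dose 1 users, so the inflation is 1/s: 1.05, 1.11 and 1.25 for s = 0.95, 0.90 and 0.80.

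**Step 6. What the alternative keeps.** Grouping Week 4 values by the site of dose 1 keeps all of them, about 50 to 55 subjects.

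**The case against.** **The loss may be small.** This stands. The documents give no switching rate, and the Instructions for Use are not among them. Subjects may have a settled preference, and the upper arm is open only to caregivers, with one caregiver allowed per subject, which ties site to user. At s = 0.95 only about 10% is lost. A reader might infer that much of the Week 4 data is thrown away; nothing in the documents supports that.

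**Nothing leaves the report.** Largely right. Excluded subjects stay in the overall and baseline-use summaries. For PK they also appear in Figure 8.1, which marks the site of each dose, and in the concentration and exposure listings. None of these summarises Week 4 by dose 1 site, and SAP Table 5 plans no individual eosinophil display.

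**Week 4 is not a clean single-dose reading for everyone.** Correct. Subjects on mepolizumab at entry had at least 12 weeks of prior dosing, which contributes to their Week 4 value. The single-dose reading is clean only among non-users, a stratum the SAP already separates. Later study sites are irrelevant to the Week 4 sample in both strata.

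**The SAP only fills in a detail.** The protocol does not say how to classify subjects who change site, and Protocol 9.3 leaves full details to the analysis plan. A reader might infer that the SAP contradicts the protocol; that goes too far. Still, dropping subjects from a planned summary is a narrowing that SAP 2.1 should record.

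**A constant cohort suits profiles over time.** This stands. Mixing all subjects at Week 4 with a subset at later visits on one line would mislead, so the remedy should be a separate Week 4 display.

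**Conclusion.** The concern holds in a limited form. The same-site rule covers Week 4, where it has no pharmacological basis, and it selects Week 4 values on site choices made after sampling. That follows from the timing alone and does not depend on any switching rate.

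The size cannot be fixed from the documents. Under the assumed models the share kept is 90%, 81% or 64% (s = 0.95, 0.90, 0.80), or 73%, 52% or 25% (independent choice at 90/10, 80/20, 50/50). These figures take switching as unrelated to the Week 4 value; if it is related, the subset is also biased, in a direction the documents do not allow one to state.

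Two further readings are tempting and should be resisted. The pooled factor 1/√(share kept), which gives 1.17, 1.39 and 2.00 for the three independent-choice cases, is not in general the inflation for a site mean; that is 1/p and differs by site. Nor does the rule as written cut Week 4 harder than other visits, since it uses one subset throughout. What sets Week 4 apart is that the exclusion is wholly avoidable there.

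The consequence is minor. PK and eosinophils are other endpoints, all analyses are descriptive, and the primary endpoint is unaffected.

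**What to change.** 1. Add a Week 4 summary of plasma concentration, and one of eosinophils (absolute and ratio to baseline), by site of dose 1 and baseline mepolizumab use, for all subjects in the PK and PD populations respectively.
2. Keep the same-site subset for the profiles over time and for the Week 8 and Week 12 summaries.
3. Record the same-site restriction in SAP 2.1 as a change from Protocol 9.4.3 and 9.4.4, with carry-over between doses as the reason.

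The cost is a few extra displays built from data already collected. The Week 4 cohort will differ from that at later visits, so the new tables need a label saying so. Cells may be small: three sites by two baseline-use strata make six cells for about 50 subjects, which is a further reason not to shrink them at Week 4.

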9. BLOOD EOSINOPHILS

Blood eosinophil analyses will be based on the “Pharmacodynamic” population.

9.1. Overview of Planned Analyses for Blood Eosinophils

- Blood eosinophil values will be \log_e -transformed prior to summarising. Non-detectable values of 0 GI/L, will be replaced by half of the lowest observed detectable (non-zero) value in the study data set, prior to log transformation.
- Blood eosinophil values will be summarised by visit, and by visit and baseline mepolizumab use.
- Blood eosinophil values will also be summarised by visit, baseline mepolizumab use and injection site. These summaries will be performed only for the subset of subjects using the same injection site throughout the study.

Table 5 provides an overview of the planned analyses for blood eosinophils. Full details of data displays to be presented are given in Appendix 8: List of Data Displays.

Table 5 Overview of Planned Analyses for Blood Eosinophils

Endpoint	Untransformed						Log-Transformed							
	Stats Analysis			Summary		Individual		Stats Analysis			Summary		Individual	
	F	T	L	F	T	F	L	F	T	L	F	T	F	L
Absolute Blood Eosinophils					Y						Y	Y		
Ratio to Baseline Blood Eosinophils					Y						Y	Y		

NOTES :

- T = Table, F = Figures, L = Listings, Y = Yes display generated.
- Stats Analysis = Represents TFL related to any formal statistical analyses (i.e. modelling) conducted.
- Summary = Represents TFL related to any summaries (descriptive statistics) of the observed raw data.
- Individual = Represents FL related to any displays of individual subject observed raw data.

10. EXACERBATIONS

Analyses of exacerbations will be based on the “All Subjects (Safety)” population. The number and percentage of subjects with at least one on-treatment exacerbation will be summarised. On-treatment exacerbations are defined in Section 14.2.1.2. All exacerbation data will be listed.

11. SAFETY ANALYSES

The safety displays to be created as part of this RAP include all the required and relevant displays identified as per the IDSL Core Safety Statistical Displays.

Analysis of safety data will be based on the ‘All Subjects (Safety)’ population.

11.1. Overview of Planned Adverse Event Analyses

Table 6 provides an overview of the planned analyses of AE data. Full details of the data displays to be presented are given in Appendix 8: List of Data Displays.

Table 6 Overview of Planned Adverse Event Analyses

Endpoint / Parameter/ Display Type	Absolute		
	Summary		Individual
	T	F	L
Adverse Events (AEs)			
All AEs by SOC	Y		Y
Common AEs by Overall Frequency ^[1]	Y		
No. of Subjects & No. of Occurrences of Common AEs by SOC and PT ^[1]	Y		
All AEs by SOC and Maximum Intensity	Y		
All Drug-Related AEs by SOC	Y		
All Drug-Related AEs by SOC and Maximum Intensity	Y		
AEs by Week 12/Early Withdrawal Binding Antibody Result (see Section 12)	Y		
AEs Leading to Permanent Discontinuation of Study Treatment or Withdrawal from Study by Overall Frequency	Y		Y
AEs reported on the Day of Dosing ^[2]	Y		Y
Subject Numbers for Individual AEs			Y
Relationship Between AE SOC, PT & Verbatim Text			Y
Serious AEs (SAEs) and Other Significant AEs			
Fatal SAEs by Overall Frequency	Y		Y
All SAEs by SOC	Y		
Non-Fatal SAEs			Y
Reasons for Considering as a SAE			Y
Drug-Related Fatal SAEs by Overall Frequency	Y		
Drug-Related SAEs by SOC	Y		
No. of Subjects & No. of Occurrences of All SAEs	Y		
Adverse Events of Special Interest (AESI)			
Anaphylaxis	Y		Y
Systemic Reactions – Allergic (Type I Hypersensitivity) and Other Systemic	Y		Y
Systemic Reactions – Allergic (Type I Hypersensitivity)	Y		Y
Systemic Reactions – Other Systemic	Y		Y
Local Injection Site Reactions	Y		Y
Opportunistic Infections	Y		Y
Malignancies	Y		Y
Serious Cardiac, Vascular and Thromboembolic Events	Y		Y
Serious Ischemic Events	Y		Y

NOTES :

- T = Table, F = Figure, L = Listing, Y = Yes display generated, SOC = System Organ Class, PT = Preferred Term.
- Summary = Represents TFL related to any summaries (i.e. descriptive statistics) of the observed raw data.
- Individual = Represents FL related to any displays of individual subject observed raw data.

^[1] Common AEs will be defined as AEs with frequency $\geq 3\%$ (prior to rounding to nearest percent) in either the Total Liquid or Lyophilised Vial treatment groups.

^[2] AEs reported on the day of dosing will be defined as adverse events with a start date equal to the date of dosing.

11.1.1. Adverse Events of Special Interest

Adverse events of special interest (AESIs) are adverse events associated with the identified and potential risks of mepolizumab. AESIs reported by the investigator as anaphylaxis reactions, systemic reactions (further categorised by the investigator as either allergic (type I hypersensitivity) or other systemic reactions) and local injection site reactions are collected via targeted eCRF within the study.

AESIs of opportunistic infections, malignancies, serious cardiac vascular and thromboembolic (CVT) events and serious ischemic events will be identified from a list of relevant preferred terms maintained within a project level reference dataset created based on the MedDRA dictionary available at the time of database freeze for this study. Further details of how relevant preferred terms are identified are given in the Program Safety Analysis Plan (PSAP).

Separate summary tables showing the number and percent of subjects with each type of AESI, broken down by preferred term will be created.

For each type of AESI a profile summary table will be produced containing information including, but not be limited to, the number of occurrences of the event, event characteristics, time to onset, intensity, outcome and action taken.

Separate listings of AESIs identified by the investigator as anaphylaxis, allergic (type I hypersensitivity), other systemic reactions and local injection site reactions will be produced, as well as listings of opportunistic infections, malignancies, serious CVT events and serious ischemic events.

